### 10.1.5 Response Review

N/A

## 10.2 Secondary Outcome

Patient: symptom experience, spiritual distress, prognostic awareness, health care utilization, and mortality. Caregiver: Quality of life, caregiver burden, spiritual distress, and prognostic awareness.

### 10.2.1 Relevant Subset

All participants will be assessed for secondary outcomes.

### 10.2.2 Measurement Definition

Secondary outcomes are

Patient—mood symptoms (PROMIS-29), spiritual distress (FACIT—Spiritual Well-being), symptom experience (Edmonton Symptom Assessment Score), prognostic awareness (questions adapted from the CANCORS study), health care utilization (# of post-operative hospitalizations and/or emergency room visits), mortality, and self-described experiences and thoughts about surgeon-PC team co-management.

Caregiver—mood symptoms (PROMIS-29), spiritual distress (FACIT—Spiritual Well-being), prognostic awareness (questions adapted from the CANCORS study), caregiver burden (Zarit Caregiver Burden Scale—ZBI-12), and self-described experiences and thoughts about surgeon-PC team co-management.

	Study design	Participants	Outcomes and Measurement Times
SA1 (months 1-36)	Randomized controlled trial (n=420 patients; Approx. n = 304 family members); Outcomes measured at approximately: - enrollment - 1 week after surgery - 1 month after surgery - 3 months after surgery - 6 months after surgery	Patients	(1) Quality of life - Functional Assessment of Chronic Illness – Palliative Care (FACIT-Pal)** Subscales: (i) Functional Assessment of Cancer Therapy (FACT-G) (ii) Trial Outcome Index (TOI) (2) Demographics (3) Edmonton Symptom Assessment Score (ESAS)* (4) Functional Assessment of Chronic Illness Therapy – Spiritual Well-being (FACIT-Sp-12)* (5) Mood symptoms including anxiety and depression subscales – PROMIS-29 (6) Health care utilization* (# of post-operative hospitalizations and/or emergency room visits) (7) Presence of advance care planning* (8) Prognostic understanding* (9) Mortality*
		Family members/Companions	(1) Demographics (2) Zarit Caregiver Burden Scale (ZBI-12)* (3) Mood symptoms including anxiety and depression subscales – PROMIS-29 (4) Functional Assessment of Chronic Illness Therapy – Spiritual Well-being (FACIT-Sp-12) family/companion measure* (5) Prognostic understanding*

### 10.2.3 Measurement Methods

- Patient – mood symptoms (PROMIS-29), spiritual distress (FACIT—Spiritual Well-being), symptom experience (Edmonton Symptom Assessment Score), prognostic awareness (questions adapted from the CANCORS study), healthcare utilization, mortality, and self-described experiences and thoughts about surgeon-PC team co-management.

- Caregiver—mood symptoms (PROMIS-29), spiritual distress (FACIT—Spiritual Well-being), prognostic awareness (questions adapted from the CANCORS study), caregiver burden (Zarit Caregiver Burden Scale—ZBI-12), and self-described experiences and thoughts about surgeon-PC team co-management.

### 10.2.4 Measurement Time Points

The secondary outcome will be assessed at baseline during enrollment, one week after surgery, one month after surgery, 3 months after surgery, and 6 months after surgery. Participants will have a window of +/- 7 days to complete the surveys for each timepoint before it is considered “missed.”

### 10.2.5 Response Review

N/A

## 11. MULTISITE REGULATORY CONSIDERATIONS

The Stanford Cancer Institute Data and Safety Monitoring Committee (DSMC) will be the monitoring board for this study, please refer to the [Data and Safety Monitoring Committee SOP](#) for more information.

### 11.1 Monitoring plan

The Stanford Cancer Institute Data and Safety Monitoring Committee (DSMC) will be the monitoring entity for this study. The DSMC will audit study-related activities approximately once per year to determine whether the study has been conducted in accordance with the protocol, local standard operating procedures, FDA regulations, and Good Clinical Practice (GCP). This may include review of the following types of documents participating in the study: regulatory binders, case report forms, eligibility checklists, and source documents. In addition, the DSMC will regularly review serious adverse events and protocol deviations from all sites associated with the research to ensure the protection of human subjects. Results of the DSMC audit will be communicated to the IRB and the appropriate regulatory authorities at the time of continuing review, or in an expedited fashion, as needed.

### 11.2 Protocol Review and Amendments

The protocol, the proposed informed consent and all forms of participant information related to the study (e.g. advertisements used to recruit participants) will be reviewed and approved by the Stanford IRB and Stanford Cancer Institute Scientific Review Committee (SRC). Any changes made to the protocol will be submitted as a modification and will be approved by the IRB prior to implementation. The Protocol Director will disseminate the protocol amendment to all participating investigators. Investigators will be expected to obtain IRB approval within 90 days for all amendments.

### 11.3 Data management

The electronic dataset and recordings are stored on an encrypted computer that is password protected with a secure server. All paper copies of the consent form are stored in a locked filing cabinet. During the data collection period, only the study team has access to the Stanford-hosted REDCap database that contains protected health information.

All data will be stored in HIPAA compliant Stanford Medicine Box and/or REDcap. All electronic devices used to store study data, including but not limited to: computers, smartphones, tables, external hard disks USB drives, etc. that any hold identifiable participant data will be password protected, backed, up and encrypted per Stanford policy. All participants will be given a unique identifier number with data storage linked to the UIN and all data stored in a password-protected, secure database.

## 11.4 Study Documentation

The Protocol Director and participating site investigators must maintain adequate and accurate participant case histories with observations and other data pertinent to the study. Original source documents should be transcribed to Case Report Forms (CRFs) and used to communicate study data to the lead site. Source documents include informed consent forms and electronic medical data.

Participating Center's PIs will be responsible for maintaining the clinical protocol and subjects' study charts, reporting adverse events, assuring that consent is obtained and documented, and reporting the status of the trial in continuing renewals submitted to their IRB and trial monitoring group(s) as per their facility protocol.

## 11.5 Site Communication

Teleconferences are convened weekly between all sites to discuss participants and study-related matters; calls may also occur more frequently if needed. Teleconferences are coordinated by the Stanford site coordinator and include study PI and all research coordinators. Any issues with patient compliance, database entry, or other items will also be discussed in these calls. Once a month, the call includes the study PI, all research coordinators, and all study site PI's.

# 12. STATISTICAL CONSIDERATIONS

Since funding in 2017, this study has been in collaboration with the Palliative Care Research Cooperative (PCRC), which is based out of the University of Colorado in Denver. The initial study biostatistician was [name] of Stanford University but [name] departed from Stanford. Consequently, through the study team's longitudinal relationship with the PCRC, the current study biostatistician is [name], MSPH, Assistant Research Professor at the University of Colorado Anschutz Medical Campus in Denver, CO.

## 12.1 Statistical Design

Differences in primary and secondary outcomes between intervention and control arms will be evaluated at each individual time point as well as across the intervention period.

### 12.1.1 Randomization

Randomization occurs immediately after enrollment. Participants are stratified by study site. Using the REDCap database, group assignment (intervention or control) is determined via a computer-generated random allocation with a block size of 6. Patients, caregivers, and surgeons cannot be blinded to group assignment due to practical considerations; however, the principal investigator and analysis team are blinded to participant randomization. The research team collecting outcome data are blinded to participant randomization, whenever possible.

## 12.2 Interim analyses

No interim analyses will be conducted.

## 12.3 Descriptive Statistics and Exploratory Data Analysis

Descriptive statistics will be calculated to summarize patients' characteristics and other baseline variables. Comparability of the intervention arm and the control arm will be assessed with regard to preintervention sociodemographic and health status measures derived from the Medical Record Abstraction. Although randomization should account for such differences, a two-sample t-test/Mann-Whitney test will be performed to investigate the differences between intervention and control group for continuous variables and Fisher's exact test or chi-squared test will be used to investigate differences between intervention and control group for binary or categorical variables.

For primary and secondary outcomes, based in the type of the data, summary univariate (descriptive) statistics (e.g., mean, standard deviation, median, interquartile range, maximum, minimum, count, percentage) will be determined for all outcomes stratified by group assignment. Descriptive time trend plots (multiple visits) stratified by group assignment will be presented for outcomes that are measured at multiple visits to allow for the visual comparison of change patterns before and after the intervention.

## 12.4 Primary Analysis

The primary outcome for this study is quality of life three months following surgery.

### 12.4.1 Analysis Population

Our study will use an intent-to-treat approach in which all data from study patients in both intervention and control arms are used, regardless of the level of adherence to the study arm.

### 12.4.2. Analysis Plan

The effect of group assignment (intervention or control) on the quality of life will be tested. Differences in outcomes between two arms at each visit will be tested by the two-sample t-test/Mann-Whitney test or Fisher's exact test/chi-squared test based on the data types of the outcomes. The effect of intervention on the quality of life after accounting for various confounding variable will be determined using a linear mixed model that accounts for within-subject variations due to repeated measures. Sensitivity analyses will assess whether there are differential effects on contingent on patient or study site characteristics on the primary outcomes.

The overall level of statistical significance was set at  $p<0.05$ . For all models, the research team will identify possible confounding variables for model adjustment, including baseline attributes. Using peer-reviewed literature, the research team has identified confounding variables that models will be adjusted for. These covariates include patient gender, age, race, education, and health status.

Qualitative data related to secondary outcomes will be transcribed, de-identified, and analyzed

based on qualitative description. A HIPPA-compatible, professional transcription service will be used for interview transcription. NVivo software will be used for qualitative analyses. A codebook will be determined by a three-person team with a single coder then analyzing the transcripts. Line-by-line, axial, and theoretical consensus coding will be used to organize and summarize findings, which will be validated through triangulation, member checking, and search for disconfirming data.

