### 12.6.2 Sample size justification

It is hypothesized that surgeon-palliative care co-management (intervention) perioperative palliative care will improve patient postsurgical quality of life as compared to surgeon-alone management of care (control). Thus, the null hypothesis is that the intervention and control groups will not differ in postsurgical quality of life measures.

The estimated sample size is 186 patients per arm or 372 patients total (380 patients was our goal). The sample size and power of this study was based on the primary outcome quality of life measure, FACIT-Pal. With this sample size, using an unpaired two-sample t-test, the present study is powered to detect an anticipated small-to-moderate effect size of 0.4 at 12 weeks with 90% power and probability type I error of 0.05 (two-sided). This power analysis includes a 86% participant completion rate as well as a variance inflation factor of 20%.

One of the study sites had a study coordinator abruptly quit the position in 2019 and consequently data on 20 participants from that site were compromised. Following the same methodological approach described in the published protocol paper (which anticipated a LTFU rate of 14%), we performed a re-estimate of the required sample size for this study in December 2020 and discovered that it was higher than anticipated (28%) due to the study coordinator turnover and interruptions caused by the pandemic. This was discussed with the funder (PCORI); the study team and PCORI had consequently agreed to target 420 enrollees to ensure sufficient sample size and study power. However, in December 2021, we re-evaluated our LTFU rate and found that it had markedly improved during the most recent year of enrollment and was now the same as was originally anticipated. In communication with PCORI, we returned the enrollment rate to 380.

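### Section 12.4.2 does not say which result decides the primary hypothesis: unadjusted per-visit tests and an adjusted mixed model with no stated 3-month contrast share one 0.05 level

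*Combined protocol and SAP*

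**What the plan says.** The endpoint and its time are clear. Section 12.4 states: "The primary outcome for this study is quality of life three months following surgery". Section 1.1 gives the same outcome at 12 weeks.

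Section 12.4.2 then describes two analyses of that outcome:

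- Unadjusted: "Differences in outcomes between two arms at each visit will be tested by the two-sample t-test/Mann-Whitney test". The choice between tests depends on data type, which does not separate a t-test from a Mann-Whitney test for a continuous score.
- Adjusted: "The effect of intervention on the quality of life after accounting for various confounding variable will be determined using a linear mixed model". No visit term, arm-by-visit term or 3-month contrast is given.

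Neither is called primary. One level covers both ("The overall level of statistical significance was set at" p<0.05), with no order or split. Section 12.1 adds that differences "will be evaluated at each individual time point as well as across the intervention period". The null hypothesis in 12.6.2 names no time point.

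On covariates, 12.4.2 says that "the research team will identify possible confounding variables for model adjustment, including baseline attributes". Its next sentence says that confounders have already been identified from the literature, followed by: "These covariates include patient gender, age, race, education, and health status". Baseline FACIT-PaL and site are not expressly among the five. Section 12.3 gives medical record abstraction as the source of preintervention health status, but no single measure is chosen.

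The only text that ties one test to one time point is the sample size justification: "using an unpaired two-sample t-test, the present study is powered to detect an anticipated small-to-moderate effect size of 0.4 at 12 weeks". Section 12.6.3 repeats it.

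**The concern.** A confirmatory trial needs one result that decides the primary hypothesis, fixed before the data are seen by arm. Here at least two candidates are planned at the same level: the t-test (or Mann-Whitney test) at 3 months and the mixed-model arm effect. If they disagree, the plan does not say which one counts. If a positive result from either could be reported as success, the type I error exceeds 5%.

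There is also a question of what is estimated. A mixed model with an arm term but no arm-by-visit term estimates an effect averaged over visits. That equals the 3-month difference only if the effect is constant over the averaged visits. The text permits such a model and does not require it.

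**Working it through.** **1. The plan's own figure.** Inputs from 12.6.2 and 12.6.3: effect size 0.4, two-sided 0.05, 90% power, variance inflation 1.20, completion 0.86. The exact two-sample t-test needs 132.3, so 133 per arm. Then 133 × 1.20 = 159.6, and 159.6 / 0.86 = 185.6, which rounds to the stated 186 per arm (372 total). The sizing therefore matches one unadjusted t-test at 12 weeks. Working back, 186 × 0.86 / 1.20 = 133.3 effective patients per arm.

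**2. Type I error if either of two results may carry the claim.** Treat the two test statistics as standard normal under the null with correlation c, each tested at |z| > 1.96. The error is 1 − P(|Z1| ≤ 1.96 and |Z2| ≤ 1.96), from the bivariate normal distribution. The documents give neither the variance explained by covariates (R²) nor the correlation between visits (ρ), so both are assumed.

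| Second result beside the 3-month t-test | c | Assumption | c value | Error |
|---|---|---|---|---|
| 3-month test adjusted for named covariates | √(1 − R²) | R² = 0.01 | 0.995 | 5.5% |
| | | R² = 0.02 | 0.990 | 5.7% |
| | | R² = 0.05 | 0.975 | 6.0% |
| 3-month test adjusted for baseline FACIT-PaL | √(1 − ρ²) | ρ = 0.3 | 0.954 | 6.4% |
| | | ρ = 0.5 | 0.866 | 7.3% |
| | | ρ = 0.8 | 0.600 | 8.8% |
| Mean of the 3 visits up to 12 weeks | √((1 + 2ρ)/3) | ρ = 0.3 | 0.730 | 8.2% |
| | | ρ = 0.5 | 0.816 | 7.7% |
| | | ρ = 0.8 | 0.931 | 6.7% |
| Mann-Whitney test at 3 months | √(3/π) | normal data | 0.977 | 6.0% |

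A simulation of the first case (133 per arm, five covariates, 20,000 null trials) gave 5.8% at R² = 0.01 and 6.4% at R² = 0.05, where the t-test alone gave 5.1% and 5.2%. The excess is about 0.7 to 1.2 percentage points, of the same order as the formula.

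**3. Power of the two candidate primary tests at 0.4 SD.** With n = 133.3 per arm, power ≈ Φ(d√(n/2) − 1.96), and √(n/2) = 8.164.

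- Unadjusted t-test: 0.4 × 8.164 = 3.266; power about 90%.
- Adjusted for baseline, ρ = 0.3: d = 0.4/√(1 − 0.09) = 0.419; 0.419 × 8.164 = 3.42; power about 93%.
- Adjusted for baseline, ρ = 0.5: d = 0.4/√(1 − 0.25) = 0.462; 0.462 × 8.164 = 3.77; power about 96%.

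**The case against.** The best defence is that the documents already point to one test. The endpoint and time are fixed, and the unpaired t-test is the only test tied to 12 weeks, two-sided 0.05 and 90% power. The order in 12.4.2, between-arm test first and adjusted effect second, fits a primary test with an adjusted companion. On that reading 5% holds and only a sentence of designation is missing. The principal investigator and analysts are also blinded to allocation (2.4, 3.5, 12.1.1), which limits choosing by result before unblinding.

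Most of this stands, and it limits the weight of the point. It does not close it. A power basis is not a decision rule, and 12.4.2 does not refer to it. Section 12.4.2 also uses the mixed model to determine the adjusted effect, and 12.5.2 uses nearly the same wording for the secondary outcomes, so nothing marks out a primary test. Blinding does not settle which result counts once the data are unblinded. The published protocol paper cited in the document was not available and might name the test.

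A reader might infer three stronger things that the documents do not support:

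- That success at any of the four postoperative visits would count. With independent tests the error would be 1 − 0.95⁴ = 18.5%. Section 12.4 fixes 3 months, so this does not follow.
- That the covariate list is wholly open. The plan says that confounders have been identified and names five. What remains is a conflict between adjacent sentences and an unchosen health-status measure.
- That the mixed model will average over visits and so may miss an effect seen only at 3 months. The model is unspecified, and this is one possible reading of it.

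**Conclusion.** The concern holds as a specification gap of modest size. Section 12.4.2 names no deciding result, although the sizing text leans towards the 12-week t-test. The inflation arises only if either of two results may carry the claim. With the covariates the plan names, it is about half to one percentage point (5.5% to 6.0%). It grows to 6.4% to 8.8% only if the model adjusts for baseline FACIT-PaL, which 12.4.2 allows as a baseline attribute but does not name, and to 6.7% to 8.2% only if the model averages visits. All these ranges rest on assumed R² or correlation and on normal theory. Apart from error rates, a visit-averaged effect would not be the quantity that 12.4 names. The sample size itself is sound. This should be fixed, but it does not undermine the design.

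**What to change.** Before unblinding, amend 12.4.2 to name one primary test at two-sided 0.05. The preferred choice is the arm difference at 3 months from the mixed model already planned, with visit and arm-by-visit terms. Adjust it for baseline FACIT-PaL (already collected), site (already the stratification factor) and the five listed covariates, with one baseline health-status measure chosen. Replace the two conflicting covariate sentences with this closed list. Label the per-visit tests, including the 12-week t-test used for sizing, the other visits and the across-period effect as supportive.

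Naming only the 12-week t-test would also hold 5% and would match the sizing exactly. It forgoes the precision of baseline adjustment: about 90% power at 0.4 SD, against about 93% to 96% for assumed correlations of 0.3 to 0.5.

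The cost is a protocol amendment with IRB approval before implementation and investigators' IRB approval within 90 days (11.2). The preferred primary analysis would differ from the t-test used for sizing, and the sponsor gives up a choice among tests. No new data and no change in sample size are needed.

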### **12.6.3 Effect size justification**

The means, standard deviations, and effect sizes were based on previous research  supporting that patients receiving medical oncologist-palliative care co-management had better quality of life (measured by Functional Assessment of Cancer Therapy – Lung; FACT-L) than patients receiving medical oncologist alone management. Mean score differences in FACT-L were  $98.0 \pm 16.7$  ( $n = 74$ ) in the intervention group and  $91.5 \pm 16.5$  ( $n = 77$ ) in the control group resulting in an effect size of 0.42 (unpaired two-sample t-test). Since the FACIT-Pal scale used in this study is a direct corollary of the FACT-L scale, this effect size was used to estimate the sample size for the present study. The sample size and power of this study are based on the quality of life measure, FACIT-Pal. Based on the unpaired two-sample t-test, the present study was powered to detect an anticipated small-to-moderate effect size of 0.4 at 12 weeks with 90% power and probability type I error of 0.05 (two-sided). Patients will be nested within the four intervention sites, which will introduce some within-site correlation that could decrease the efficiency of these estimators. Thus, a variance inflation factor of 20% was incorporated in the sample size estimation. Additionally, it is predicted that this study will have missing data due to patients discontinuing participation in the study and death. Based both on the research team's past experiences conducting studies in this population and already published perioperative mortality data, we assumed a dropout rate of 11% and a mortality rate at 12 weeks of 3%; thus, patient completion rate was estimated to be 0.86. Together, with the assumptions outlined here, the estimated sample size needed for the present study is a total of 186 patients per arm (372 patients total) and our goal was to recruit 380 patients.

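### No planned analysis shows whether the three-month FACIT-Pal result survives informative dropout: the primary test is not named and the sensitivity analyses are effect-modification tests

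*Combined protocol and SAP*

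**What the plan says.** Section 12.4 sets the primary outcome as quality of life three months after surgery. Section 12.4.2 then gives two kinds of analysis. The first is by visit: "Differences in outcomes between two arms at each visit will be tested by the two-sample t-test/Mann-Whitney test" (or a categorical test where the data type requires it). The second is a covariate-adjusted model, "a linear mixed model that accounts for within-subject variations due to repeated measures". Both fall under one significance level of 0.05, and neither is named as primary. Sections 12.6.2 and 12.6.3 base the sample size on the unpaired t-test.

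The one sentence on sensitivity analyses is "Sensitivity analyses will assess whether there are differential effects on contingent on patient or study site characteristics on the primary outcomes".

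Section 12.4.1 describes intent-to-treat: "all data from study patients in both intervention and control arms are used, regardless of the level of adherence to the study arm". Section 10.1.4 defines when a survey counts as missed.

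The plan expects missing outcomes. Section 12.6.3 says "it is predicted that this study will have missing data due to patients discontinuing participation in the study and death", and "we assumed a dropout rate of 11% and a mortality rate at 12 weeks of 3"%, giving a completion rate of 0.86. These figures are used only to enlarge the sample. Section 12.6.2 reports three loss figures: 14% anticipated; 28% found in December 2020, attributed to coordinator turnover and the pandemic; and, in December 2021, a return to the anticipated rate after a marked improvement in the latest year of enrolment. It also says that data on 20 participants at one site were compromised.

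**The concern.** A sensitivity analysis for missing data asks whether the conclusion holds when the assumption about unseen scores is relaxed. Asking whether the effect differs by patient or site characteristics is a different question, and its answer says nothing about unseen scores. No section states a missing-data assumption, plans an analysis that departs from missing at random, or says how deaths before three months enter the quality-of-life comparison.

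Loss related to quality of life is plausible here. Patients and surgeons know the allocation (sections 3.5 and 12.1.1), only the intervention arm has scheduled palliative care contacts (section 4), the surgeon may withdraw a patient without stated criteria (section 4.2), and death is an expected cause of loss. Enlarging the sample protects power but does not remove bias. With two candidate tests and no named primary, the choice between an available-case result and a missing-at-random result is also left open until the data are seen.

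**Working it through.** **The plan's own sample size.** Inputs from sections 12.6.2 and 12.6.3: effect 0.4 SD, two-sided alpha 0.05, power 90%, variance inflation 1.20, completion 0.86. The t-test needs 132.3, so 133 per arm. 133 × 1.20 / 0.86 = 185.6, so 186 per arm and 372 in total. This matches the plan.

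**Power under non-informative loss.** With 380 enrolled (190 per arm), t-test power for 0.4 SD is 90.8% at 14% loss (about 53 patients missing) and 85.2% at 28% loss (about 106 missing). Power stays reasonable across the documented range, so what remains open is bias.

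**Tipping point.** Assumptions: the effect estimated under missing at random is 0.4 SD; loss L is equal in the two arms; missing intervention patients score delta SD worse than that analysis implies; missing controls are not shifted; the standard error is held at its value for patients with data.

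- Effective n per arm = 190(1 − L) / 1.20
- SE = √(2 / effective n)
- Threshold for significance = 1.96 × SE
- Effect after the shift = 0.4 − L × delta
- Tipping delta = (0.4 − threshold) / L

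| Loss | Effective n per arm | SE | Threshold | Tipping delta |
|---|---|---|---|---|
| 14% | 163.4 / 1.2 = 136.2 | 0.121 | 0.238 | (0.4 − 0.2375) / 0.14 = 1.16 SD |
| 21% | 150.1 / 1.2 = 125.1 | 0.126 | 0.248 | (0.4 − 0.2478) / 0.21 = 0.73 SD |
| 28% | 136.8 / 1.2 = 114.0 | 0.132 | 0.260 | (0.4 − 0.2596) / 0.28 = 0.50 SD |

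The 21% row is only the midpoint of the other two. A t critical value in place of 1.96 gives 1.15, 0.72 and 0.50 SD. Leaving out the 20% variance inflation gives 1.31, 0.83 and 0.58 SD.

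**Size of the dilution.** For delta of 0.25, 0.5 and 1.0 SD, the 0.4 SD effect falls to 0.365, 0.33 and 0.26 at 14% loss, and to 0.33, 0.26 and 0.12 at 28% loss.

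**Two limits.** If missing controls are also shifted, only the difference between the two shifts counts: the effect becomes 0.4 − L × (delta in intervention − delta in control), and equal shifts cancel. The table also counts deaths among the shifted patients. If 3 of the 14 points are deaths and are set aside, the missing share among survivors is 0.11 / 0.97 = 0.113, and the tipping delta rises to 0.1625 / 0.1134 = 1.43 SD.

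**The case against.** The strongest reply is that 28% is a superseded figure. A reader might infer that the trial has lost 28% of its patients and that a moderate departure would overturn its result. The documents do not support that. The 28% dates from December 2020, and section 12.6.2 says loss had returned to the anticipated rate a year later. It does not say whether the later rate is cumulative or for the latest year alone, so 14% to 28% is a range and the upper end is not the final loss. The stated causes of the excess are also largely administrative, so shifting every missing patient at 28% is a harsh case. At 14% the result is fairly robust. All of this stands.

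Three further replies stand too:

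- A reader might infer that the per-visit tests contradict the intent-to-treat statement. Section 12.4.1 frames that approach by adherence and promises no outcome for patients who gave none. A per-visit test uses everyone observed at that visit.
- A reader might infer that control patients have no palliative care contact. Section 4 lets the surgeon consult the palliative care team at any time in that arm, so only scheduled contact is exclusive to the intervention.
- The mixed model can use partial follow-up and is valid under missing at random, so the plan has some implicit handling of dropout. Delta adjustment is one acceptable method among several.

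The one-sided shift is an illustration; nothing in the documents fixes its direction. None of these replies supplies an analysis that departs from missing at random, a rule for deaths, or a named primary test.

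**Conclusion.** The concern holds as a gap in the plan. Section 12.4.2 does not name the primary analysis, and no planned analysis would show whether the three-month FACIT-Pal result survives informative dropout. Under the stated assumptions, the shift that removes significance is about 1.15 SD at 14% loss and about 0.5 SD at 28% loss. The result could be fairly robust or fragile across the documented range, and the plan has no means of showing which. A smaller observed effect would tip sooner; similar shifts in both arms would matter less.

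The sizes are given in SD units because the means and standard deviations in section 12.6.3 come from FACT-L, not FACIT-Pal. The calculation quantifies a significant result only. It does not show that dropout was informative or that any result is wrong.

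**What to change.** In section 12.4.2:

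1. Take the primary inference from the mixed model's three-month treatment contrast, using every available FACIT-Pal score. State its missing-at-random assumption and make the per-visit tests descriptive.
2. Add a delta-adjusted multiple-imputation (tipping-point) analysis of three-month FACIT-Pal among patients alive at three months. Set the shifts in SD units, vary them separately by arm, and extend them until the conclusion changes. Report deaths before three months and handle them separately instead of imputing scores for them.
3. Report loss by arm and reason, and label the differential-effect tests as subgroup or interaction analyses.

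The cost is SAP wording and a little extra programming. No new data are needed.
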